#### **Treatment period**

Study day 1 through 30 days after the last administration of investigational product.

#### **Treatment-emergent Adverse Events (TEAE)**

Treatment-emergent adverse events (TEAE) are defined as any adverse event **occurring after first dose through 30 days after last dose of talimogene laherparepvec**. Adverse events that occur on the same day as the first dose date of IP will be treated as treatment emergent events unless indicated otherwise (for example, if an event occurs on the same date as the first administration of talimogene laherparepvec and the check box indicating prior to the first dose of IP is checked on eCRF, then the event will not be counted as a treatment-emergent AE. Additionally, if an event is identified as disease-related on the eCRF, it will not be counted as a treatment-emergent AE).

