9. SAFETY DATA COLLECTION, RECORDING, AND REPORTING

9.1 Definition of Safety Events

9.1.1 Disease-related Events

Disease-related events are events (serious or non-serious) anticipated to occur in the study population due to the underlying disease. These could include events such as pain or discomfort caused by growing tumors due to overall worsening of disease. Such events do not meet the definition of an Adverse Event unless assessed to be more severe than expected for the subject's condition or if the investigator believes that the event is related to the investigational product(s), study treatment, or protocol required therapies. Further, any disease-related event which meets any of the seriousness criteria in [Section 9.1.3](#) should be **recorded** as a Serious Disease-related Event **and reported to the sponsor or designee within 24 hours**.

Note: For situations where disease-related events are due to squamous cell cancer of the head and neck (SCCHN), the primary tumor type (eg, metastatic SCCHN) should be used, rather than the term "disease progression".

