9.1.3 Serious Adverse Events

A serious adverse event is defined as an adverse event that meets at least 1 of the following serious criteria:

- fatal
- life-threatening (places the subject at immediate risk of death)
- requires in-patient hospitalization or prolongation of existing hospitalization
- results in persistent or significant disability/incapacity
- congenital anomaly/birth defect
- other medically important serious event

A disease-related event (eg, PD or pain or discomfort caused by growing tumors) is to be reported as a serious adverse event if

- the subject’s pre-existing condition becomes worse than what the investigator would consider typical for a subject with the same underlying condition, or
- if the investigator believes a causal relationship exists between the investigational medicinal product(s)/protocol-required therapies and the event,
- and the event meets at least 1 of the serious criteria above.

Approved

An adverse event would meet the criterion of “requires hospitalization”, if the event necessitated an admission to a health care facility (eg, overnight stay).

If an investigator considers an event to be clinically important, but it does not meet any of the serious criteria, the event could be classified as a serious adverse event under the criterion of “other medically important serious event”. Examples of such events could include a new cancer that is not a condition of the study, events associated with an overdose, allergic bronchospasm, convulsions, blood dyscrasias, DILI (see [Appendix A](#) for DILI reporting criteria), or events that necessitate an emergency room visit, outpatient surgery, or urgent intervention.

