9.2 Safety Event Reporting Procedures

9.2.1 Reporting Procedures for Disease-related Events

The investigator is responsible for ensuring that all disease-related events (serious or nonserious) observed by the investigator or reported by the subject that occur after the first dose of talimogene laherparepvec through the safety follow-up visit (ie, 30 [+ 7] days after the last dose of talimogene laherparepvec), are **recorded** using the Event CRF as a Disease-related Event.

All serious disease-related events will be recorded and reported to the sponsor or designee within 24 hours. The investigator will submit any updated serious disease-related event data to the sponsor within 24 hours of it being available.

The investigator must assign the following attributes to each disease-related event:

- disease-related event diagnosis or syndrome(s), if known (if not known, signs or symptoms)
- dates of onset and resolution (if resolved)
- severity (and/or toxicity per protocol)
- assessment of relatedness to talimogene laherparepvec
- action taken

CTCAE version 4.0 will be used to grade a disease-related event. The grading scale used in this study is described in [Appendix A](#).

Note: If the event is more severe than expected for the subject’s condition or if the investigator believes there is a causal relationship between the investigational product(s)/study treatment/protocol required therapies and disease worsening, the event should be reported as an adverse event, not a disease-related event. The investigator is

expected to follow reported disease-related events (serious or non-serious) until stabilization or reversibility.

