#### **Treatment-related emergent Adverse Events**

**Treatment-related adverse events are defined as treatment-emergent adverse events which are considered to be related to the treatment of talimogene laherparepvec, as determined by the investigator.**

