### **10.6.2 Adverse Events**

The Medical Dictionary for Regulatory Activities (MedDRA) version **23.0** or later will be used to code all adverse events (AE) to a system organ class and a preferred term. The CTCAE version 4.0 will be used to grade severity of adverse events. In general, events with missing IP relatedness, seriousness, or CTCAE severity grades are included in the analysis of treatment emergent AE as long as the event meets the criteria for a TEAE. However, analyses of treatment-related, SAE, or grade 3 or higher, or combination thereof will exclude events with missing relatedness, seriousness, and severity grades, respectively.

The analyses for AEs will include TEAEs (ie, occurring in the treatment period) unless otherwise specified. The subject incidence of TEAEs will be summarized for all AEs, serious AEs, AEs leading to withdrawal of investigational product, grade 3 or 4 AEs, and fatal AEs. The subject incidence of all treatment-related AEs, serious AEs, AEs leading to withdrawal of investigational product, grade 3 or 4 AEs, and fatal AEs will be tabulated by system organ class (SOC) and preferred term in descending order of frequency. A listing of fatal AEs will be provided. A listing of all SAEs reported in the clinical database with an event onset from consent will be provided with onset reported relative to the first and most recent dose of study therapy and identification as a TEAE.

Subject incidence of DREs (disease-related events), fatal disease related events, serious disease-related events, and disease-related events leading to withdrawal from study will be tabulated by system organ class and preferred term.

Treatment-related AEs reported in long term follow-up will be summarized in this study and analyzed at a program-level.

Potential or known unintended exposure to talimogene laherparepvec, related suspected signs or symptoms, and detection of exposure to talimogene laherparepvec in a subject's household member, caregiver, or healthcare provider will be reported to Amgen. Exposures, signs or symptoms will be summarized in this study and analyzed at a program-level.

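### The SAP excludes every event flagged disease-related from the treatment-emergent and treatment-related AE tables, with no exception for one still marked as related to the product at lock

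*SAP*

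**What the plan says.** SAP Section 6 defines treatment-emergent AEs by timing and then adds that "if an event is identified as disease-related on the eCRF, it will not be counted as a treatment-emergent AE". No condition is attached. The same section builds the next category on that one: "Treatment-related adverse events are defined as treatment-emergent adverse events which are considered to be related to the treatment of talimogene laherparepvec".

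The protocol lists the attributes an investigator must assign to each disease-related event (Section 9.2.1). One of them is "assessment of relatedness to talimogene laherparepvec".

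The protocol also says where product-related events belong. Under Section 9.1.1 a disease-related event counts as an AE in only two situations: when its severity goes beyond what the illness would explain, and "if the investigator believes that the event is related to the investigational product(s), study treatment, or protocol required therapies". Section 9.2.1 repeats the rule for suspected causal links to disease worsening: "the event should be reported as an adverse event, not a disease-related event". Section 9.1.3 sends an event to SAE reporting "if the investigator believes a causal relationship exists between the investigational medicinal product(s)/protocol-required therapies and the event" and a seriousness criterion is met.

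Events left as disease-related get their own output. SAP 10.6.2 tabulates "Subject incidence of DREs (disease-related events), fatal disease related events, serious disease-related events" and those leading to withdrawal, by system organ class and preferred term. Protocol 10.4.2 plans similar summaries. Neither document mentions a breakdown by relatedness.

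**The concern.** The documents use two fields for the same question, and the SAP reads only one of them. The disease-related flag decides whether an event enters the AE tables. The relatedness answer on the same record is ignored once that flag is set. If the two disagree at lock, the SAP follows the flag, while Protocol 9.1.1 makes the investigator's belief about causality decisive.

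The distinction is a hard one in this trial. The protocol's example of a disease-related event is "pain or discomfort caused by growing tumors due to overall worsening of disease". The product is injected into tumors, and Protocol 6.2.1.1 expects that tumors may grow before benefit is seen. That text is there to justify the response criteria, not to guide AE attribution, but it shows that drug and disease effects can look alike. There is no control arm in which a misattribution would show up.

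At stake is the incidence of adverse events, which is the trial's safety endpoint. For a doubly marked record, the exclusion can only lower the treatment-emergent and treatment-related counts.

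**Working it through.** The plan gives no figure to reproduce. The check is to follow a disease event that the investigator believes is product-related through the rules.

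**Case 1: the site follows the protocol.**
1. Protocol 9.1.1 and 9.2.1: the event is recorded as an AE, or as an SAE under 9.1.3 if serious.
2. The disease-related flag is not set, so the SAP exclusion does not apply.
3. The event counts as treatment-emergent and, being marked related, as treatment-related. Nothing is lost.

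**Case 2: the record is flagged disease-related and also marked related at lock.** This can arise from misclassification at entry, or when relatedness is updated later and the flag is left alone.
1. Protocol 9.1.1: the event meets the AE definition, because the investigator believes it is product-related.
2. SAP Section 6, treatment-emergent definition: it is excluded, because the flag is set.
3. SAP Section 6, treatment-related definition: it is excluded again, because this category is drawn from treatment-emergent AEs.
4. SAP 10.6.2: it is counted in the disease-related tables, where its relatedness is not shown.

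In Case 2 the protocol definition and the SAP derivation give opposite answers. The SAP is not silent here: an analyst applying it as written would exclude the event. SAP 9.3 and 10.6.2 say what to do when relatedness is missing, but nothing says what to do when it contradicts the flag.

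**Size.** AE tables use the safety analysis set (SAP 7.2 and 10.1), planned at 18 to 24 dosed subjects (SAP 3.2). One affected subject moves the overall treatment-related incidence by at most 1/n:
- n = 18: 1/18 = 0.0556, or 5.6 percentage points.
- n = 24: 1/24 = 0.0417, or 4.2 percentage points.

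The full shift occurs only if that subject has no other treatment-related AE; otherwise the overall row does not move. A row for a single preferred term can still change if the subject has no other counted event of that term. The documents do not say how often Case 2 would occur, so no expected total can be given.

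**The case against.** The strongest reply is that Case 2 should not exist. Three protocol sections (9.1.1, 9.1.3 and 9.2.1) send product-related events to AE or SAE reporting, so for correctly recorded data the SAP exclusion simply applies the protocol's own AE definition. Protocol 12.3 adds a data management review that checks subject data for discrepancies and protocol adherence and raises queries with the site; a doubly marked record is the sort of thing it should catch. An event that slips through is still reported, in the disease-related tables.

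Most of this stands. A reader might infer that drug-caused tumor pain disappears from the safety report by design. The documents do not support that: the loss needs a misclassified or unreconciled record, and even then the event is tabulated elsewhere.

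The reply does not remove the conflict. The routing rule instructs sites; it does not tell the analyst what to do with a record that breaches it. The review in Protocol 12.3 is general and does not name this contradiction. The disease-related tables keep the event but hide the fact that it was judged related.

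On size, it is fair to say that many subjects may already count as having a treatment-related AE. In the adult pivotal study (Protocol 2.2.2), fatigue, chills and pyrexia occurred in 50.3%, 48.6% and 42.8% of treated patients. If children are similar, which is an assumption, and if those events are mostly judged related, which that section does not say, the overall row would often stay put.

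**Conclusion.** The point holds as a conflict between an unconditional SAP flag and the protocol's AE definition, confined to disease-related events still marked related at lock. For those records the SAP gives the wrong answer in both the treatment-emergent and the treatment-related tables. The effect is at most 4.2 to 5.6 points of overall treatment-related incidence per affected subject, under the condition given above, and the number of such subjects is unknown.

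Two further inferences are tempting and are not supported:
- That the primary endpoint is biased. SAP 10.6.1 takes DLTs from the CRF, and Protocol 6.2.1.2.3 defines them by the investigator's causality judgment. Neither runs through the treatment-emergent definition, and nothing shows that disease-related events escape DLT review.
- That the minimum of nine in cohort A1 can serve as the denominator for a larger effect. That figure is a minimum of DLT-evaluable subjects, not an AE-table denominator. SAP 10.1 also calls for summaries by cohort, where one subject would weigh more than overall, but the documents do not fix the number dosed in each cohort.

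The conclusion assumes that the eCRF lets both marks stand on one record. The attribute list in Protocol 9.2.1 implies this, but the form itself is not in the documents.

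**What to change.** In SAP Section 6, limit the exclusion to events that are flagged disease-related and not marked as related to talimogene laherparepvec. Add that any disease-related event with relatedness answered yes is queried before database lock so that the site can correct the flag or the relatedness. In SAP 10.6.2, state that any such record remaining at lock counts as a treatment-emergent and a treatment-related AE.

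The cost is one derivation clause on a field already collected, plus one specific query within the existing data review. The downside is a slightly higher reported AE incidence, within the per-subject bound given above. No new table and no change to the DLT analysis are needed.

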#### **Treatment-emergent Serious Adverse Events (TESAE)**

**Treatment-emergent serious adverse events are defined as any serious adverse event occurring after initiation of the first dose of study therapy through 30 days after the last administration of study therapy.**

#### **Treatment-related emergent Adverse Events**

**Treatment-related adverse events are defined as treatment-emergent adverse events which are considered to be related to the treatment of talimogene laherparepvec, as determined by the investigator.**

#### **Treatment-related Adverse Events in Long Term Follow-up**

**Treatment -related adverse events in long term follow-up are collected after the safety follow-up visit through the end of the long-term follow-up.**

#### **Treatment-emergent Disease-related Events (TEDRE)**

Treatment-emergent Disease-Related Events (DREs) are defined as adverse events, determined by the investigator to be disease-related, with an onset during the treatment period. DREs that occur on the same day as the first dose of IP will be treated as

treatment emergent events unless indicated otherwise (for example, if an event occurs on the same date as the first administration of talimogene laherparepvec and the check box indicating prior to the first dose of IP is checked on the eCRF, then the event will not be counted as a treatment-emergent DRE).

[figure not shown]
## **7. Analysis Subsets**

[figure not shown]
### **7.1 DLT Analysis Set**

**The DLT analysis set will include DLT evaluable subjects defined as subjects who had the opportunity to be followed for at least 35 days from the initial dosing of talimogene laherparepvec and received at least two treatments of talimogene laherparepvec (except subjects who had a DLT after the first dose). Subjects may be replaced in a cohort if they are not evaluable for DLT (eg, a subject did not receive study treatment, or ended the study treatment before completion of DLT evaluation period for a reason other than experiencing a DLT).**

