6.2.1.1 Dosage, Administration, and Schedule

Talimogene laherparepvec must be prepared and administered by a qualified healthcare professional. Subjects should be assessed clinically for adverse events/toxicity prior to each dose using the CTCAE version 4 ([Appendix A](#)). Complete blood count with differential and chemistry panels including liver function laboratory tests (ALT, AST, and total bilirubin) should be obtained according to the Schedule of Assessments ([Table 3](#)) and the results should be checked before each treatment. Dosing will occur only if these test values are acceptable per [Section 6.2.1.2](#) and [6.2.1.3](#). Sedation can be used and the type and dose is up to the discretion of the investigator taking into consideration the subject's medical history, age, and site of disease. Additionally, use of pain medication (eg, acetaminophen/paracetamol/narcotic) or anti-anxiety medication (eg, benzodiazepine) as premedication to help decrease the pain or anxiety associated with the injection is acceptable and left to the discretion of the investigator. Because

flu-like symptoms are common adverse events experienced by HSV-seronegative subjects after talimogene laherparepvec treatment, premedication with the appropriate antipyretic and/or antiemetic medications prior to each talimogene laherparepvec treatment is strongly recommended to prevent the occurrence of these symptoms in the HSV-seronegative subjects. The type and dose will be up to the discretion of the investigator taking into consideration the subject's medical history and age.

Talimogene laherparepvec will be administered by intralesional injection only into injectable cutaneous, subcutaneous, nodal tumors, and other non-visceral tumors with or without image guidance. Talimogene laherparepvec must not be administered into tumor lesions in visceral organs.

The first dose of talimogene laherparepvec will be up to 4.0 mL of 10^6 PFU/mL administered on day 1. The second injection, up to 4.0 mL of 10^8 PFU/mL (or up to 4.0 mL of 10^6 PFU/mL for a dose de-escalated cohort), will be administered 21 (+ 3) days after the initial injection (ie, no sooner than day 22 but should not be delayed more than 3 days after the 21-day time point). All subsequent injections, up to 4.0 mL of 10^8 PFU/mL (or up to 4.0 mL of 10^6 PFU/mL for a dose de-escalated cohort), will be administered every 14 (\pm 3) days. The treatment cycle interval may be increased due to toxicity.

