6.2.1.2.1 Rules for DLT Evaluation

The DLT evaluation period is 35 days from the initial administration of talimogene laherparepvec. For a subject to be considered DLT-evaluable, subjects must receive 2 doses of talimogene laherparepvec (one dose of up to 4.0 mL of 10^6 PFU/mL followed by a dose of up to 4.0 mL of 10^8 PFU/mL for Dose Level 1, or 2 doses of up to 4.0 mL of 10^6 PFU/mL for Dose Level -1) during the 35 day DLT evaluation period, with the exception when a DLT occurs after the first dose. Subjects may be replaced in a cohort if they are not evaluable for DLT (ie, a subject did not receive at least 2 treatments of talimogene laherparepvec, or ended the study treatment before completion of DLT evaluation period for a reason other than experiencing a DLT).

A DLRT will review the safety data to evaluate possible drug effects and DLT. The DLRT will review the safety data of the first 3 DLT-evaluable subjects in the older age cohort (A1 or A2) to decide if the younger age cohort can be opened for enrollment. The decision to open the younger age cohort for subject enrollment will be based on < 33% DLT rate of the first 3 DLT-evaluable subjects in the older age cohort (A1 or A2) during the DLT evaluation period.

If a DLT occurs in the first 3 DLT-evaluable subjects in the older age cohort (A1 or A2), the younger age cohort will not open until a DLT rate < 33% is observed with at least 6 DLT-evaluable subjects in the older age cohort (A1 or A2). The starting dose for the younger age cohort will be Dose Level 1 (if the DLT rate in the older age cohort at Dose Level 1 is < 33%) or Dose Level -1 (if Dose Level 1 is intolerable for the older age cohort). After both cohorts are open, the DLRT will review the safety data after the earlier of the following events: (a) the addition of 3 new DLT-evaluable subjects in a cohort **until there're 9 DLT-evaluable subjects in the cohort**; (b) a DLT rate \geq 33% considering all DLT-evaluable subjects in a cohort; (c) at the occurrence of the first DLT in either cohort. **If deemed necessary, ad-hoc meetings to review the safety data can be convened anytime by the DLRT.**

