6.2.1.3 Dosage Adjustments, Delays, Rules for Withholding or Restarting, Permanent Discontinuation

Talimogene laherparepvec treatment should be continued based on the potential benefit/risk assessment of the subject.

Dose reduction within a cohort for an individual subject who experience adverse events is not allowed. If in the course of administration of talimogene laherparepvec the subject cannot tolerate the full dose due to an injection-related adverse event, the total volume given should be recorded, and the reason for intolerance should be documented as an adverse event.

If a subject experiences any of the following treatment-related toxicities, administration should be delayed until the toxicity has resolved to at least CTCAE grade 1 or baseline:

- grade 2 or greater immune-mediated adverse events, with the exception of vitiligo
- grade 2 or greater allergic reactions
- any other grade 3 or greater hematologic or non-hematologic toxicity

If the subject requires corticosteroid dosing greater than that required for maintenance physiologic replacement therapy, talimogene laherparepvec dosing should be withheld.

If a subject demonstrates evidence of new or worsening CNS metastases, all study treatments should be withheld. Resumption of talimogene laherparepvec dosing should be left to the discretion of the investigator and discussed with the Amgen medical monitor.

If talimogene laherparepvec treatment is delayed by > 1 week, that dose will be deemed to have been missed and the subject will proceed to the next scheduled treatment visit.

If talimogene laherparepvec dosing is delayed by more than 6 weeks from the date of the planned dose due to the occurrence of an adverse event that is considered related to talimogene laherparepvec, the subject must be permanently withdrawn from talimogene laherparepvec treatment. If talimogene laherparepvec dosing is delayed by more than 6 weeks from the date of the planned dose for reasons other than treatment-related toxicity, the case must be reviewed by the Amgen medical monitor in conjunction with the investigator to determine if the subject can resume talimogene laherparepvec therapy. Reason for dose change of talimogene laherparepvec is to be recorded on CRF.

Talimogene laherparepvec will be permanently discontinued for subjects meeting any of the following criteria:

- Subject developed DLT during the DLT evaluation period.

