10.1.1.4 Exploratory Endpoints

10.1.2 Analysis Sets

10.1.2.1 DLT Analysis Set

The DLT analysis set will include DLT-evaluable subjects defined as subjects who had the opportunity to be followed for at least 35 days on treatment from the initial dosing and received at least 2 treatments of talimogene laherparepvec (except subjects who had a DLT after the first dose). Subjects may be replaced in a cohort if they are not evaluable for DLT (eg, a subject did not receive study treatment, or ended the study treatment before completion of DLT evaluation period for a reason other than experiencing a DLT).

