### 2.4 Exploratory

### 3. Study Overview

#### 3.1 Study Design

This is a phase 1, multicenter, open label study of talimogene laherparepvec in pediatric subjects with advanced non-CNS tumors that are amenable to direct injection in the clinical setting.

Approximately **18 to 24** pediatric subjects are expected to be enrolled and **treated with at least 1 dose of talimogene laherparepvec** into 2 cohorts stratified by age (permissible based on the incidence of DLTs, a minimum of **18 dosed** subjects total **for the primary analysis**) as follows:

- Cohort A1 (12 to  $\leq$  21 years of age)
- Cohort B1 (2 to  $<$  12 years of age)

Initially, 3 subjects 12 to  $\leq$  21 years of age are to be enrolled and treated at 100% of the recommended adult dose regimen of talimogene laherparepvec (Cohort A1). The first dose administered will be up to 4.0 mL of  $10^6$  PFU/mL followed by a dose of up to 4.0 mL of  $10^8$  PFU/mL 21 days (+3 days) later. Subsequent doses of up to 4.0 mL of  $10^8$  PFU/mL will be administered approximately every 14 days ( $\pm$  3 days) thereafter (see protocol Section 6.2.1.1). The DLT evaluation period is 35 days from the initial administration of talimogene laherparepvec. Rules for DLT evaluation are described in Section 6.2.1.2.1 of the protocol. The dose level review team (DLRT) will review the safety data of the first 3 subjects in the older age cohort A1 to decide if the younger age cohort B1 can be opened for enrollment. If none of the first 3 DLT-evaluable subjects in cohort A1 experiences a DLT then cohort B1 will be opened for enrollment and treatment at the same dose level per the section Study Design and Treatment Schema of the protocol. If a DLT occurs in the first 3 DLT-evaluable subjects in the older age cohort (A1 or A2), the younger age cohort will not open until a DLT rate  $<$  33% is observed with at least 6 DLT-evaluable subjects in the older age cohort (A1 or A2). If any of the first 3 subjects in cohort A1 experiences a DLT, the DLRT will make a recommendation on whether an additional 3 subjects should be enrolled in cohort A1.

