### **11. Changes From Protocol-specified Analyses**

**In order to define DLT evaluable subjects consistently with protocol section 6.2.1.2.1, definition of DLT analysis set is updated in statistical analysis plan section 7.1 from protocol section 10.1.2.1. Subjects who had the opportunity to be followed for at least 35 days from the initial administration of talimogene laherparepvec and received at least two treatment of talimogene laherparepvec, with the exception when a DLT occurs after the first dose, will be considered DLT evaluable.**

---

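### The DLT analysis set sets no time limit on the second dose, although the protocol's DLT rule requires both doses within 35 days

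*SAP*

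**What the plan says.** Four places define who is DLT-evaluable.

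- **Protocol 6.2.1.2.1** requires two doses "during the 35 day DLT evaluation period, with the exception when a DLT occurs after the first dose".
- **Protocol 10.1.2.1** takes subjects who "had the opportunity to be followed for at least 35 days on treatment from the initial dosing" and had at least two treatments, with the same exception for a DLT after dose 1. It gives no date for the second treatment.
- **SAP 7.1** takes any subject that "had the opportunity to be followed for at least 35 days from the initial dosing of talimogene laherparepvec and received at least two treatments", with the same exception. It drops the on-treatment qualifier and also gives no date.
- **SAP 11** explains the change: "In order to define DLT evaluable subjects consistently with protocol section 6.2.1.2.1, definition of DLT analysis set is updated". It then restates the SAP 7.1 definition, again without the dosing window.

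SAP 3.1 adds a cross-reference: "Rules for DLT evaluation are described in Section 6.2.1.2.1 of the protocol". SAP 10.6.1 reports the primary endpoint (frequency, percentage and exact 95% CI) on the DLT Analysis Set.

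**The concern.** SAP 11 sets out to match protocol 6.2.1.2.1, but the element of that rule missing from protocol 10.1.2.1 is the window for both doses, and it was not brought in. A programmer who follows SAP 7.1 or SAP 11 as written would count subjects whom 6.2.1.2.1 excludes.

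The error has one direction. Under protocol 6.2.1.2.3 a toxicity is a DLT only if it occurs during the evaluation period, and a DLT in that period ends treatment. Anyone who receives a second dose after the period has therefore had no DLT, and nothing that follows that dose can become one. At Dose Level 1 such a subject also had no exposure to the 10^8 PFU/mL concentration inside the window, so adds no DLT information about it. At stake is the accuracy of the reported primary rate and its agreement with the rate on which the dose level review team (DLRT) acted, in cohorts small enough for one subject to matter.

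**Working it through.** **1. The plan's own figures.** Protocol Table 5 and SAP Table 2 give the probability of declaring a cohort safe with 6 DLT-evaluable subjects. Since 2/6 = 33.3% is not below 33%, safe means at most 1 DLT. With q = 1 − p, P(safe) = q^6 + 6pq^5, which is 88.6%, 65.5%, 42.0%, 23.3% and 10.9% at p = 10% to 50%. The stated 89/66/42/23/11% reproduce. They assume that all six subjects are properly evaluable.

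**2. Can a second dose fall outside the window?** Study day d is d − 1 days after dose 1.

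- Protocol 6.2.1.1 plans dose 2 at 21 (+3) days, Days 22 to 25, "no sooner than day 22 but should not be delayed more than 3 days after the 21-day time point". The same section says: "The treatment cycle interval may be increased due to toxicity".
- Protocol 6.2.1.3 says that for listed related toxicities "administration should be delayed until the toxicity has resolved to at least CTCAE grade 1 or baseline". Some of these need not be DLTs: grade 2 immune-mediated or allergic events, and grade 3 fatigue, which 6.2.1.2.3 expressly excludes. Delays for other reasons are also foreseen.
- A delay of up to one week ends by Day 25 + 7 = Day 32 at the latest, inside the window.
- A longer delay makes the dose missed, and the subject moves to the next visit: Day 36 ± 3 (Days 33 to 39), then Day 50.
- Days 33–35 are inside. Day 36 is 35 days after dose 1, the edge. Days 37–39 (36 to 38 days) and Day 50 (49 days) are outside.

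The route is narrow but open.

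**3. Effect on the reported rate.** Let x be the DLTs, n the subjects evaluable under 6.2.1.2.1, and k the late-dose subjects. The reported rate is x/(n + k) instead of x/n. The documents give no k; 1 to 3 is assumed. Intervals are exact (Clopper-Pearson) 95%.

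| Under 6.2.1.2.1 | k = 1 | k = 2 | k = 3 |
|---|---|---|---|
| 2/6 = 33.3% (4.3–77.7) | 2/7 = 28.6% (3.7–71.0) | 2/8 = 25.0% (3.2–65.1) | 2/9 = 22.2% (2.8–60.0) |
| 3/9 = 33.3% (7.5–70.1) | 3/10 = 30.0% (6.7–65.2) | 3/11 = 27.3% (6.0–61.0) | 3/12 = 25.0% (5.5–57.2) |

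Away from the boundary the shift is small: 1/6 = 16.7% becomes 1/7 = 14.3%. With no DLTs the upper limit is 1 − 0.025^(1/n), which falls from 33.6% at 0/9 to 30.8% at 0/10.

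**4. How often is the count exactly at the boundary?** Assume reviews every 3 subjects, continuation past 3 and past 6 only with at most 1 DLT, and no over-enrollment while results are pending (which 6.2.1.2.1 in fact permits).

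- Exactly 2/6: q^3·3p^2q + (3pq^2)^2 = 12p^2q^4 = 20%, 26%, 25% at p = 20%, 30%, 40%.
- Exactly 3/9: 6pq^5·3p^2q + q^6·p^3 = 19p^3q^6 = 4.0%, 6.0%, 5.7%.

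If 1/3 = 33.3% is instead taken to stop the cohort, these become 3p^2q^4 = 4.9%, 6.5%, 6.2% and 10p^3q^6 = 2.1%, 3.2%, 3.0%. A reported rate that crosses 33% also needs a late-dose subject in the same cohort. That joint probability cannot be computed from the documents.

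**The case against.** The strongest reply is that the intent is plain: SAP 3.1 sends the reader to 6.2.1.2.1 and SAP 11 states the aim of matching it, so this is a loose paraphrase rather than a rival definition. The intent is indeed clear, but SAP 7.1 and SAP 11 each spell out a complete definition without the window, and a stated aim does not supply the missing condition.

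Second, 6.2.1.2.1 is itself untidy. Its sentence on replacing subjects describes non-evaluability as fewer than two treatments or an early end of treatment, with no time limit. That is true and should be tidied, but the sentence follows the two-doses-in-the-window requirement and does not replace it.

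Third, the route is narrow and the effect may be nil. This stands. Apart from fatigue, a related grade 3 non-hematologic toxicity lasting more than 3 days despite optimal supportive care is already a DLT, and most delayed doses would still fall inside the window.

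Fourth, no dose decision is overturned. This also stands: under 6.2.1.2.1, a rate of 33% or more seen at any time already makes the dose intolerable. The boundary probabilities are moreover start-of-trial values that depend on how 1/3 is treated. The Amendment 3 rationale reports 10 subjects already enrolled in cohort A1, so they are context only.

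Last, SAP 10.6.1 counts DLTs from the CRF and describes no check of event date against the window. A mis-recorded event could then be counted, so the non-event claim holds under the protocol's definition, not necessarily for every CRF entry.

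**Conclusion.** The concern holds and should be fixed. The operative definition of the primary-endpoint denominator omits a condition of the rule it claims to match, and the omission can only lower the reported DLT rate or leave it at zero. One late-dose subject moves the rate by 4.8 percentage points at 2/6 (33.3% to 28.6%), 3.3 at 3/9 (33.3% to 30.0%) and 2.4 at 1/6 (16.7% to 14.3%). All of these shifts are small beside the width of the exact intervals.

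The size rests on an assumed 1 to 3 late-dose subjects per cohort; with none there is no effect. It also assumes that DLTs are recorded according to the protocol's window. The consequence is confined to the reported rate and its agreement with the DLRT's figure.

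**What to change.** In SAP 7.1 and SAP 11, state that both treatments must be received during the 35-day DLT evaluation period, keeping the exception for a DLT after the first dose. State which study day ends the period, so that a Day 36 dose is classified the same way by everyone. Bring protocol 10.1.2.1 and the replacement sentence in protocol 6.2.1.2.1 into line.

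The SAP clauses alone correct the reported rate, need no new data and can be added before the analysis. A protocol change needs investigator agreement and IRB/IEC approval (protocol 12.1), so that wording can wait for the next amendment. The only analytic cost is a DLT denominator that may be slightly smaller.
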